1 QUESTIONS ABOUT THE PARTICIPANTS

- 1.1 Do you request blood culture samples to be taken for adult patients as part of your regular day-to-day work? Yes/No
- 1.2 Do you take blood culture samples for adult patients as part of your regular day-to-day work? Yes/No
- 1.3 Do you receive results from blood culture samples for adult patients in your regular day-to-day work? Yes/No
- 1.4 Which best describes the clinical setting you currently work in for the majority of your clinical time?

Acute Ward (medical) / Acute Ward (surgical) / Critical Care Unit (HDU or ICU) / Emergency Department / Other acute care setting (please specify) / I do not work in hospital acute care

[Anybody answering "no" to all of the first three questions or "I do not work in hospital acute care" to 1.4 will receive a statement that they aren't eligible for the study and will be directed to an exit page.]

- 1.5 What is your gender? Female/Male/Other/Prefer not to say
- 1.6 What is your age (in years)? years/prefer not to say
- 1.7 How do you describe your ethnicity? White/Mixed or Multiple ethnic groups/Asian or Asian British/Black, African, Caribbean or Black British/Other (please specify)/Prefer not to say
- 1.8 Which best describes your job role? Advanced Clinical Practitioner / Doctor/ Healthcare assistant/ Nurse/ Paramedic/ Phlebotomist/ Physician's Associate / Other (please specify) /Prefer not to say
- 1.9 A: For doctors only: What is your career stage? FY1/FY2/CT1/CT2/CT3/ST4+/Consultant/Other (please specify)/Prefer not to say
 B: For nurses/HCAs only: What is your current grade? Band 3/Band 4/Band 5/Band 6/Band 7/Band 8/Band 9/Other (please specify)/Prefer not to say
 C: APCs only: What is your current stage of training? Trainee / Qualified / Credentialled/Other (please specify)/Prefer not to say

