3.1.3. Eligibility criteria

Inclusion criteria:

• UK healthcare professionals whose role involves requesting blood culture samples, taking blood culture samples and/or using the results from blood cultures for adult patients with suspected severe infection.

Exclusion criteria:

- UK healthcare professionals working in neonatal or paediatric acute care or children's emergency department.
- UK healthcare professionals working outside of adult acute care.
- Healthcare professionals working outside of the UK.

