2. Engagement variables: We will assess three single-item, self-reported variables measuring how frequently healthcare staff engage in different aspects of blood culture sampling: (1) requesting samples, (2) collecting samples, and (3) using the results from samples. Variables will be measured on a 5-point likert scale (1= Never, 2 = Hardly any shift, 3 = Some shifts, 4 = Most shifts, 5 = Almost every shift, N/A = this isn't part of my job role).
 3. Barrier variables: We will assess the perceived influences of 29 barriers to blood culture sampling, measured via a 7-point likert scale ranging from 1 (strongly disagree that this factor influences blood culture sampling) to 7 (strongly agree that this factor influences blood culture sampling).

4) How many and which conditions will participants be assigned to?

We will employ a quasi-experimental design, where professional role (doctors vs. advanced clinical practitioners, nurses, paramedics & physician associates vs. healthcare assistants & phlebotomists) and clinical setting (acute medical ward vs. acute surgical ward vs. emergency department vs. critical care unit) will be treated as between-subject IVs.

5) Specify exactly which analyses you will conduct to examine the main question/hypothesis.

H1: We will run a confirmatory factor analysis to test our hypothesized factor structure and validate our attitude questionnaire in the context of blood culture sampling. We will use Maximum Likelihood for our estimation method and assess the goodness of fit of the resulting models using six key statistics: chi-square (χ 2); relative chi-square (CMIN/DF); comparative fit index (CFI); non-normed fit index (NNFI); root mean square error of approximation (RMSEA); and standardized root mean square residual (SRMR). Following identification

Combined Protocol V3.0 22/07/24

of the best model fit, four latent attitude variables will be confirmed, which will be based on the theoretical dimensions of (1) perceived importance, (2) social norms, (3) self-efficacy and (4) controllability in the context of blood culture sampling. For each of these latent variables, factor scores will be calculated by deriving the mean of all constituent variables. We will use these latent variables for our subsequent analyses.

H2a,b: We will run a 3×4 between-within subjects ANOVA to test for interactions and simple main effects of professional role and latent attitude dimension on mean attitude ratings.

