We will run a 4×4 between-within subjects ANOVA to test for interactions and simple main effects of clinical setting and latent attitude dimension on mean attitude ratings.

If significant main effects are detected for either ANOVA, we will conduct Bonferroni-corrected pairwise comparisons as follow-up analyses.

H2: We will run three multiple regression analyses, one for each of our engagement variables. For each regression analysis, predictors will be entered hierarchically in blocks.

Block 1: Demographic variables. This will include *age*, *gender* \rightarrow female/other (1), male (0); and *ethnicity* \rightarrow people of colour (1), white (0). **Block 2: Professional variables**. This will include *professional role* \rightarrow healthcare assistants & phlebotomists (2), advanced clinical practitioners, nurses, paramedics & physician associates (1), doctors (0); *clinical setting* \rightarrow acute surgical ward (3); emergency department (2); critical care unit (1); acute medical ward (0); and *seniority* \rightarrow junior (1), senior (0). **Block 3: Attitudes and beliefs**. This will include the latent attitude variables identified in our factor analysis.

H3: We will produce descriptive statistics for the influence ratings pertaining to each of the 29 barriers to blood culture sampling. We will produce an overall ranking of the 3 most influential barriers and separate rankings of barriers for different professional roles and clinical settings.

6) Describe exactly how outliers will be defined and handled, and your precise rule(s) for excluding observations.

We will exclude participants, who took less than five [revise after piloting] minutes to complete the survey. We will exclude participants, who did not complete all 20 attitude questions.

We will exclude participants suspected of "straight-lining". We will test for this separately across the 20 questions measuring attitudes and 29 questions assessing the influence of key barriers by calculating the standard deviation. Participants will be excluded from analyses if their likert ratings from either section have a standard deviation of \leq 0.45.

7) How many observations will be collected or what will determine sample size?

No need to justify decision, but be precise about exactly how the number will be determined.

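### All three Part 1b engagement regressions use seniority, but the questionnaire never collects it from paramedics, phlebotomists or physician associates

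*Protocol*

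**What the plan says.** Appendix A, item 1.8, offers seven named job roles plus two residual answers: "Advanced Clinical Practitioner / Doctor/ Healthcare assistant/ Nurse/ Paramedic/ Phlebotomist/ Physician's Associate / Other (please specify) /Prefer not to say". Item 1.9 then asks about grade or stage in three branches: A, "For doctors only: What is your career stage"; B, "For nurses/HCAs only: What is your current grade"; and C, "APCs only: What is your current stage of training". The label in branch C is read here as advanced clinical practitioners. No other item in Appendix A asks about seniority.

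Appendix 2, item 4, defines the role groups as "doctors vs. advanced clinical practitioners, nurses, paramedics & physician associates vs. healthcare assistants & phlebotomists". Item 5 states: "We will run three multiple regression analyses, one for each of our engagement variables". It lists these regressions under H2, although they address hypothesis H3. Block 2 contains role, clinical setting and seniority, the last coded "junior (1), senior (0"). The appendix does not say how grade or stage maps to that code, which value a role without an item receives, or what happens when a predictor is missing. Its exclusion rules concern completion time, unanswered attitude items and straight-lining. Section 4.1 describes this appendix as the survey's full analysis plan (calling it Appendix B).

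**The concern.** The plan gives three roles a place in the role variable and then requires a second predictor that the form does not collect from them. Without an unwritten rule, they cannot enter a model that contains both. If they leave, the role groups in the regressions are not those in the ANOVAs, although the labels are the same. Phlebotomists, whose job is taking blood, would be absent from the regression on how often staff collect samples.

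A later analysis document cannot fully repair this, because the gap is in data collection. Section 3.1.4 says that responses will not be identifiable and that no names, email addresses or identification numbers are stored with them. A question that was not asked therefore cannot be followed up.

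**Working it through.** **Step 1. Questionnaire against analysis plan.** Roles come from item 1.8, branches from item 1.9, and role codes from Appendix 2, item 5, Block 2.

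| Role (item 1.8) | Branch of 1.9 | Role code | Seniority collected? |
|---|---|---|---|
| Doctor | A | 0 | yes |
| Advanced clinical practitioner | C | 1 | yes |
| Nurse | B | 1 | yes |
| Paramedic | none | 1 | no |
| Physician associate | none | 1 | no |
| Healthcare assistant | B | 2 | yes |
| Phlebotomist | none | 2 | no |

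Four of seven named roles have a source for seniority and three have none. Respondents who answer Other or prefer not to give a role are not routed to 1.9 either, but they have no role code in the first place.

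**Step 2. Is seniority part of the planned model?** The sample-size text (section 3.1.1; Appendix 2, item 7) states 10 predictors. Entering each listed variable once gives age, gender, ethnicity (3) + role, setting, seniority (3) + four attitude dimensions (4) = 10. Without seniority it is 9. If role (three levels) and setting (four levels) are both dummy-coded, the count is 3 + 2 + 3 + 1 + 4 = 13 with seniority and 12 without. So when role and setting are treated alike, only a count that includes seniority gives the stated 10.

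**Step 3. Reproduce the stated sample size.** Inputs are α = .01, power .80, 10 predictors and effect .15, read as f² (the document writes f).

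Power(N) = P[F′(10, N − 11; λ = 0.15 N) > F₀.₉₉(10, N − 11)].

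The smallest N with power of at least .80 is 160 (power .801), which matches the stated 160. With 9 predictors (seniority dropped) the requirement is 154. With 13 (dummy coding) it is 176.

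**Step 4. Who is left under complete-case regression.** In any step containing seniority:
- code 2 becomes healthcare assistants only;
- code 1 becomes nurses and advanced clinical practitioners;
- code 0 is unchanged.

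Block 1 alone does not contain seniority. A test of R² change compares nested models on the same respondents, however, so in practice the three roles leave Block 1 as well.

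**Step 5. Effect on power.** The documents give no role mix, so the number lost is unknown. From the recruitment ceiling of 400, the share that would have to be lost before N falls to 160 is 1 − 160/400 = 60%. Taking 250 usable responses as a pessimistic illustration (the lower end of the 250–350 range cited for questionnaire validation), it is 1 − 160/250 = 36%. Three roles outside the doctors, nurses and healthcare assistants named in the lay summary are unlikely to reach either share.

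**The case against.** The strongest reply is that the drop-out is inferred. Nothing in the protocol specifies listwise deletion, and the derivation of junior/senior could be settled later, for example by assigning one level to a whole role from item 1.8. It is correct that drop-out is only the default result. But assigning seniority by role would be a new rule, would carry no information on grade within the role, and would be partly collinear with role, which is already in Block 2.

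A second reply stands in part. Items 2.1–2.3 allow a not-applicable answer for tasks outside the job. A phlebotomist who neither requests cultures nor uses results has no score on those two outcomes anyway, so for that person item 1.9 costs only the collection model. These answers, and the options not to disclose age, gender, ethnicity or grade, already make the regression samples differ from the ANOVA sample. Item 1.9 adds a systematic loss by role; it is not the only source of difference.

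Three stronger readings are tempting but not supported:
- A reader might infer that these roles vanish from the whole survey analysis. They do not: the factor analysis, both ANOVAs and the barrier rankings do not use seniority.
- A reader might infer that the study becomes underpowered. The figures above do not show that.
- A reader might add that the exclusion "Healthcare professionals working outside of the UK" also cannot be applied, because the questionnaire has no country item. That is a separate matter. The landing page, with its information sheet and consent items, is not shown and may cover it.

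**Conclusion.** The mismatch between item 1.9 and Block 2 is on the face of the document and holds. Under complete-case analysis, paramedics, phlebotomists and physician associates leave every step of the three regressions that contains seniority. The damage is to coverage and to the meaning of two of the three role groups, most clearly in the model for collecting samples. It is confined to a secondary research question; the primary questions on attitudes, and on how they differ by role and setting, are untouched.

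The conclusion rests on three assumptions: that no unwritten rule supplies seniority by role, that complete-case regression is used, and that branch C means advanced clinical practitioners. The statement on power also assumes that the effect of .15 is f². No count of lost respondents can be given, because the documents contain no role mix. The point is worth correcting because the remedy is small and the missing answers cannot be recovered afterwards.

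**What to change.** If the form can still be changed, extend item 1.9B to paramedics, phlebotomists and physician associates. Leave advanced clinical practitioners on 1.9C so that nobody is routed to two scales. State in Appendix 2 where the junior/senior cut falls on each of the three scales. The model keeps 10 predictors and the requirement of 160. The cost is one branching change and an ethics notification.

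If the survey has already opened, remove seniority from the common model and test it only within the roles that were asked. All roles in the stated groups then stay eligible for the regressions, and the requirement on the same calculation is 154. The cost is that the common model is no longer adjusted for seniority. The documents do not settle which case applies: the planned study period starts on 14 July 2024, the combined protocol is dated 22/07/24, and Appendix 2 says that no data have yet been collected.

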2 QUESTIONS ABOUT PROFESSIONAL ENGAGEMENT IN BLOOD CULTURE SAMPLING

Please answer the following questions about your engagement in blood culture sampling for acute medical adult patients with suspected severe infection. Severe infections broadly refer to infections severe enough to require IV antibiotic treatment. There are no right or wrong answers and your responses will be completely anonymous.

- 2.1 In the last month, how often have you requested blood culture samples to be taken for acute adult medical patients with suspected severe infection?
 1= Never, 2 = Hardly any shift, 3 = Some shifts, 4 = Most shifts, 5 = Almost every shift, N/A = this isn't part of my job role.
- 2.2 How often do you collect blood culture samples for acute adult medical patients with suspected severe infection?
 1= Never, 2 = Hardly any shift, 3 = Some shifts, 4 = Most shifts, 5 = Almost every shift, N/A = this isn't part of my job role.
- 2.3 How often do you **use** blood culture results to inform your treatment for acute adult medical patients with suspected severe infection?

1= Never, 2 = Hardly any shift, 3 = Some shifts, 4 = Most shifts, 5 = Almost every shift, N/A = this isn't part of my job role.

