3 QUESTIONS ABOUT BELIEFS AND ATTITUDES

Please answer the following questions about your personal opinions in the context of blood culture sampling for acute adult medical patients with suspected severe infection. There are no right or wrong answers and we are simply interested in your personal attitudes. Please rate your agreement with the questions using the following rating scale:

- 1 = Strongly disagree
- 2 = Disagree
- 3 = Somewhat disagree
- 4 = Neither agree or disagree
- 5 = Somewhat agree
- 6 = Agree
- 7 = Strongly agree

[Questions 3.1-3.20 will be presented in fully randomised order to each participant. Questions for reverse-coding are italicised.]

Attitudes pertaining to the general importance of blood culture sampling

- 3.1 In my role, blood culture sampling benefits patients with suspected severe infections.
- 3.2 Obtaining blood culture samples is a valuable activity that influences treatment choices in patients with suspected severe infection.
- 3.3 The difficulties of obtaining meaningful blood culture samples outweigh the benefits.
- 3.4 I sometimes feel that obtaining blood culture samples is not worthwhile.
- 3.5 Compared to other clinical tasks, I find the activities involved in obtaining blood culture samples to be unpleasant.

Perceptions of subjective norms

- 3.6 Colleagues I respect make time to request or collect blood cultures.
- 3.7 Obtaining blood cultures for every patient with suspected severe infection is part of our normal working culture within my unit of work.
- 3.8 Colleagues I respect value timely blood culture sampling in patients with suspected severe infection.
- 3.9 I feel under pressure from colleagues to prioritise other activities over obtaining blood culture samples for patients with suspected severe infection.

3.10 Where I work, blood culture sampling is not considered valuable for patients with suspected severe infections.

Perceived behavioural control (self-efficacy)

- 3.11 In my experience, there are many practical difficulties in obtaining timely blood culture samples.
- 3.12 I do not feel confident requesting or collecting blood cultures or using blood culture results.
- 3.13 Blood culture sampling is a routine procedure of little technical difficulty.
- 3.14 I often struggle to obtain blood culture samples from patients.
- 3.15 I have not received adequate training or guidance for activities related to blood culture sampling.

Perceived behavioural control (controllability)

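### Survey items 2.1-2.3 ask only about medical patients although surgical-ward staff are surveyed and compared, so literal answers under-report surgical-ward engagement

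*Protocol*

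**What the plan says.** All references are to the Part 1b survey protocol and its appendices.

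- **Who is surveyed.** Section 3.1.3 admits staff requesting or taking blood cultures, or "using the results from blood cultures for adult patients with suspected severe infection". The primary research question, screening items 1.1-1.3 and the introduction to the barrier section (Appendix A, section 4) also speak of adult patients without a medical restriction.
- **Settings.** Item 1.4 offers "Acute Ward (medical) / Acute Ward (surgical) / Critical Care Unit (HDU or ICU) / Emergency Department" and a further category for other acute settings.
- **Engagement items.** The Appendix A section 2 stem reads: "Please answer the following questions about your engagement in blood culture sampling for acute medical adult patients with suspected severe infection". Each item repeats the limit: 2.1 asks "how often have you requested blood culture samples to be taken for acute adult medical patients with suspected severe infection", 2.2 "How often do you collect blood culture samples for acute adult medical patients with suspected severe infection", and 2.3 concerns the use of "blood culture results to inform your treatment for acute adult medical patients with suspected severe infection".
- **Attitude items.** The section 3 introduction asks for "your personal opinions in the context of blood culture sampling for acute adult medical patients with suspected severe infection". None of the 20 items below it contains the word *medical*.
- **Analysis.** Under Appendix 2, item 4, professional role and "clinical setting (acute medical ward vs. acute surgical ward vs. emergency department vs. critical care unit) will be treated as between-subject IVs". Item 5 tests attitude ratings by setting in a 4×4 ANOVA. It also enters setting in Block 2 of three regressions, one per engagement item, with acute medical ward coded 0 and acute surgical ward coded 3. (Item 2 calls the engagement hypothesis H3; item 5 lists these regressions under H2.)

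No text tells surgical staff to answer for their own patients, and the analysis plan does not address the mismatch.

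**The concern.** Item 1.4 makes respondents choose between a medical and a surgical ward. Shortly afterwards, section 2 asks how often they culture medical patients, so the questionnaire itself sets up the contrast. A surgical-ward nurse can truthfully say yes to taking cultures from adult patients in item 1.2 and then, again truthfully, report a low frequency in item 2.2.

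The three engagement items are the outcomes of the three regressions. If surgical staff report on a narrower set of patients than they treat, a lower surgical score may reflect the wording and not practice. For these respondents the outcome also concerns medical patients, while several attitude predictors refer to their own role, unit or workplace. Once collected, a true *Never* and one produced by the wording cannot be told apart.

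**Working it through.** The plan states no figure on this point, so the first check is to set the wording side by side.

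| Place | Patients referred to |
|---|---|
| Section 3.1.3, primary research question | adults, suspected severe infection |
| Screening items 1.1-1.3 | adults |
| Section 2 stem and items 2.1, 2.2, 2.3 | acute adult **medical** patients |
| Section 3 introduction | acute adult **medical** patients |
| The 20 attitude items | no medical restriction; several tied to own role, unit or workplace (3.1, 3.7, 3.10, 3.11) |
| Section 4 introduction (barriers) | adults, suspected severe infection |

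The restriction is therefore in every engagement item, only in the introduction to the attitude items, and nowhere in the barrier section.

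**Illustrative size for engagement.** Inputs, none from the documents: surgical staff truly average 3 (*Some shifts*); a fraction q, unrelated to true frequency or attitudes, answers 1 (*Never*) because of the wording.

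1. Observed surgical mean = (1 − q) × 3 + q × 1 = 3 − 2q, a fall of 2q.
2. With σ² the variance of the true answers, the observed variance in this group is (1 − q)σ² + q(1 − q)(3 − 1)². The second term comes only from how the question was read.
3. Any attitude slope within this group is multiplied by (1 − q), because the literal readers all score 1.

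| q | Fall in mean, 2q | Reading variance, 4q(1 − q) | Slope retained, 1 − q |
|---|---|---|---|
| 0.10 | 0.2 | 0.36 | 90% |
| 0.25 | 0.5 | 0.75 | 75% |
| 0.50 | 1.0 | 1.00 | 50% |

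If setting is entered as separate categories, the surgical-versus-medical coefficient takes up the fall in mean, but the reading variance and the flatter slope remain. The plan lists codes 0 to 3 and does not say whether they are categories or one numeric term. In either case the surgical shift enters the setting estimate.

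**The case against.** The strongest reply is that the consequence is narrow, and most of it stands.

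- **Primary question.** A reader might infer that the primary comparison of attitudes by setting is confounded with wording. The documents do not support that. Only the introduction says *medical*, and items such as 3.7 and 3.10 ask about the respondent's own unit or workplace. This is a risk, not a demonstrated bias.
- **Critical care and the emergency department.** A reader might extend the point to them. Nothing in the documents suggests that their staff do not treat acute medical patients.
- **Loss through N/A.** A reader might infer that surgical respondents drop out of the models by ticking N/A. That option is defined by job role, so someone who takes cultures in regular work has little reason to choose it.
- **Setting is not the engagement hypothesis.** The hypothesis is that attitudes predict engagement; setting is a Block 2 covariate, and no ANOVA of engagement by setting is planned. The shift is therefore not an error in a primary contrast.
- **Size.** Both q and the true mean of 3 are assumed. Item 1.4 asks about the majority of clinical time, so some surgical-ward staff may also see medical patients.
- **Intent.** The programme elsewhere describes its interest as acute medical patients (the rationale sections and the co-design workshops). A medical focus may be deliberate, but Part 1b does not say so, and it would not fit an eligibility rule and setting factor that include surgical wards.

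None of this removes the restriction from items 2.1-2.3.

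**Conclusion.** The wording is inconsistent, and it matters for surgical-ward answers to the three engagement items. Answered literally, these items under-report surgical-ward activity, bias the setting coefficient and add error to the outcome in the engagement regressions. The fall in the surgical mean is unknown; it would be 0.2 to 1.0 points on the 5-point scale for q from 10% to 50%, given an assumed true mean of 3 and literal answers of *Never*. For the attitude ANOVA the wording is a lesser risk of unknown size and direction. The barrier ratings are unaffected. The point merits correction before launch because analysis cannot recover the missing information and the edit is small.

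**What to change.** **Before launch:** in the section 2 stem, items 2.1-2.3 and the section 3 introduction, replace the reference to acute medical adults with the patient description in section 3.1.3, that is, adults with suspected severe infection.

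**If medical patients are intended:** state this in Part 1b, and leave acute surgical ward out of the setting comparison and the engagement models.

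**If the survey has already opened:** keep the wording, since changing it midway would split the data. Report the surgical-ward engagement results with this limitation and add a sensitivity analysis of the three regressions without surgical-ward staff.

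**Cost:** a few words in the questionnaire and a minor ethics amendment, with no extra participants. The timing needs checking. Appendix 2 says no data have been collected, but Part 1b is dated 25-06-2024, its study period starts on 14 July 2024 and the combined protocol is dated 22/07/24, so the survey may already be open.

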APPENDIX 2 - Analysis plan

1) Have any data been collected for this study already?

No, no data have been collected for this study yet.

2) What's the main question being asked or hypothesis being tested in this study?

Q1. Does our newly developed attitude questionnaire capture key components of the Theory of Planned Behaviour within the context of blood culture sampling?

Q2. What are NHS healthcare professionals' attitudes towards blood culture sampling for adult patients with suspected severe infection? Do these attitudes differ by professional role and clinical setting?

Q3. What are predictors of self-reported engagement in clinical activities that form part of the blood culture pathway?

Q3. What are perceived barriers to healthcare staff engaging in clinical activities related to blood culture sampling for managing suspected severe infection? Do these perceived barriers differ by professional role or clinical setting?

H1. Healthcare staff's attitudes around blood culture sampling will map on to a four-factor structure proposed by the Theory of Planned Behaviour: (1) perceived importance, (2) social norms, (3) self-efficacy and (4) controllability.

H2a. There will be significant differences between the mean ratings of the four attitude dimensions.H2b. Individuals' professional roles and the clinical setting they work in will have a significant effect on their ratings of the four attitude dimensions.

H3. The four attitude dimensions will be significant predictors for self-reported engagement in the requesting of blood cultures, collection of blood culture samples and use of blood culture results.

H4. Perceptions of the most influential barriers to blood culture sampling will differ across professional roles and clinical settings.

3) Describe the key dependent variable(s) specifying how they will be measured.

1. **Attitude variables:** We will assess beliefs and attitudes pertaining to blood culture sampling via 20 authordesigned questions, created to capture different attitude dimensions that are modelled on the Theory of Planned Behaviour. Each attitude question will be measured on a 7-point likert scale ranging from 1 (strongly disagree) to 7 (strongly agree).

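### Part 1b: the requesting item asks about the last month while the collecting and using items state no period, so differences between the three engagement outcomes may partly reflect question wording

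*Protocol*

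**What the plan says.** Appendix A, section 2 has three engagement items. Item 2.1 reads "In the last month, how often have you requested blood culture samples to be taken". Item 2.2 reads "How often do you collect blood culture samples for acute adult medical patients with suspected severe infection". Item 2.3 asks, also in the present tense and without a period, how often the respondent uses "blood culture results to inform your treatment for acute adult medical patients with suspected severe infection". The section's introduction sets no common period. All three items share one response scale, "1= Never, 2 = Hardly any shift, 3 = Some shifts, 4 = Most shifts, 5 = Almost every shift", plus a not-applicable option for people whose job does not include the activity.

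Appendix 2, question 3 defines the outcomes together: "We will assess three single-item, self-reported variables measuring how frequently healthcare staff engage in different aspects of blood culture sampling". It gives no recall period. H3 also takes them together: "The four attitude dimensions will be significant predictors for self-reported engagement in the requesting of blood cultures", followed by collection and use of results. Under question 5 the plan states "We will run three multiple regression analyses, one for each of our engagement variables", with the same three predictor blocks for each. (That paragraph is labelled H2, but its content is the test of H3.)

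**The concern.** A report on last month and an undated report, most naturally read as usual practice, are different measurements. Someone who was off clinical shifts for the whole of last month can truthfully answer 'Never' to 2.1 and still give a usual frequency to 2.2 and 2.3. The not-applicable option does not catch this person, because it concerns job role. Nor does the eligibility screen, because items 1.1 to 1.3 ask about regular day-to-day work.

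The three sets of results will probably be read side by side, since H3 names all three activities and the outcomes are presented as "measuring how frequently healthcare staff engage in different aspects of blood culture sampling". If one mean is lower, or one set of attitude coefficients weaker, a reader cannot tell a real difference between steps of the pathway from a difference in what was asked. No later analysis can recover a reference period that the item did not specify.

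**Working it through.** **1. The items side by side.**

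| Item | Activity | Period stated | Tense | Scale |
|---|---|---|---|---|
| 2.1 | requesting | last month | past | 1–5 + N/A |
| 2.2 | collecting | none | present | 1–5 + N/A |
| 2.3 | using results | none | present | 1–5 + N/A |

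Nothing in Appendix 2 explains, harmonises or adjusts for the difference.

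**2. The plan's own figure.** The only stated number tied to these regressions is N = 160 (section 3.1.1 and Appendix 2, question 7): α = .01, power .80, 10 predictors, effect .15. I used the noncentral F test for an R² increase, with λ = f²N, df1 = 10 and df2 = N − 11. Reading .15 as f², N = 160 gives power 0.801 and N = 159 gives 0.797, so the stated figure reproduces. It does not depend on the time frame and is not in dispute.

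**3. How large a wording effect could be.** The documents do not give the fraction of respondents with an atypical month or say how such a month would change an answer. Both are assumptions here.

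*Model.* Usual score = round(3 + 0.45x + e), with x and e standard normal, limited to 1–5. A fraction q of respondents, unrelated to x, has an atypical month. Then f² = R²/(1 − R²). Without any atypical months, R² = .155 and f² = .155/.845 = .183. I ran this as a simulation of 2,000,000 respondents.

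| q | Atypical answer | R² | f² as % of true | Change in mean |
|---|---|---|---|---|
| 5% | one category lower | .149 | 96% | −0.05 |
| 10% | one category lower | .144 | 92% | −0.09 |
| 20% | one category lower | .136 | 86% | −0.18 |
| 5% | one category up or down at random | .149 | 95% | 0 |
| 10% | one category up or down at random | .143 | 91% | 0 |
| 20% | one category up or down at random | .132 | 83% | 0 |
| 5% | 'Never' | .125 | 78% | −0.10 |
| 10% | 'Never' | .103 | 63% | −0.20 |
| 20% | 'Never' | .073 | 43% | −0.40 |

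The last three mean shifts check by hand: q × (3 − 1) = 0.10, 0.20 and 0.40.

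*Second parametrisation.* Suppose a share s of the variance of the last-month answer is specific to that month and unrelated to the predictors. Standardised slopes then shrink by √(1 − s) and R² by (1 − s). Starting from the plan's f² = .15, R² = .15/1.15 = .130.

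| s | √(1 − s) | R² | Power at N = 160 |
|---|---|---|---|
| 0 | 1 | .130 | .80 |
| 5% | .975 | .124 | .77 |
| 10% | .949 | .117 | .73 |
| 20% | .894 | .104 | .64 |
| 30% | .837 | .091 | .54 |

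Both illustrations put the extra noise in item 2.1 only. That too is an assumption.

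**The case against.** The strongest case on the other side has five parts.

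- **No planned comparison.** The plan fits one regression per outcome, H3 asks whether attitudes predict each, and predictors of engagement are a secondary research question. This stands: each regression is interpretable for its own item.
- **The mechanism is narrow.** The scale is per shift, so someone away for part of the month can answer for the shifts worked. Scoring 'Never' because of absence plausibly needs a whole month off clinical work, and a screen on regular day-to-day work makes that group less likely to be large. This stands, and it makes the 'Never' rows close to a worst case.
- **The direction is not known.** A reader might infer that only requesting carries this error, that the other two regressions are unaffected, and that attitudes will look like weaker predictors of requesting. The documents do not support that. Items without a period carry their own recall error, and respondents may carry 'last month' forward from 2.1 to the two items that follow it.
- **Job-role subsets differ anyway.** Each item has its own not-applicable option, so the three regressions run on different staff whatever the wording. This stands, and a common period will not remove it.
- **Harm to co-design is speculative.** One might infer that co-design would act on a spurious ranking of pathway steps. Section 3 of the Part 1c/2 protocol names potential barriers as the survey's contribution, and section 6.2 refers only generally to Part 1 findings. Neither describes such a ranking.

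None of this explains why the three items differ, and none of it gives a reason to keep them different.

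**Conclusion.** The inconsistency is real: one item is dated, two are not, and the analysis plan treats them as the same kind of measure. Differences between the three outcomes may partly reflect wording. Whether they do, in which direction and by how much cannot be derived from the documents.

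With an assumed 5% to 20% of atypical respondents, f² for requesting would be about 96% to 86% of its true value if answers fall one category, and 78% to 43% if all score 'Never'. These ranges rest on the assumed fraction, the assumed response and noise confined to item 2.1. They show what is possible and are not estimates.

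This is a cheap improvement to the questionnaire. It does not invalidate any single regression or the sample size.

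**What to change.** Before fielding, give all three items the same reference period, in one of two ways:

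- ask all three about the last month in the same past-tense form, and add to each an option for people who worked no clinical shifts in that month, set to missing; or
- ask usual frequency in all three.

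State the chosen period in the definition of the engagement variables in Appendix 2, question 3. When reporting, note that the three regressions also rest on different job-role subsets.

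The cost is rewording one or two items, plus the extra option if the last month is kept, in an online form. Appendix 2 states that no data have been collected. However, the Part 1b front matter records ethical approval, so an amendment may be needed. The planned period also starts on 14 July 2024, before the combined protocol's date of 22/07/24, so fielding may already have begun. In that case leave the items as they are, report the differing time frames as a limitation and do not compare the three regressions.
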